11.8.3 Efficacy Analyses

Between-treatment comparisons with respect to the change from baseline in LVEF and the change from baseline in myocardial strain at Month 6 and Month 12 will be performed for the ITT and PP Populations using the Wilcoxon rank sum test. A supportive analysis with missing LVEF at Month 12 imputed by LVEF at Month 6; subjects missing LVEF at both Month 6 and Month 12 will be excluded from this supportive analysis. In line with the current paradigm for the assessment of therapeutic efficacy in rare diseases and specifically DMD using established natural history data ([Liu 2022](#), [US FDA 2019](#), [US FDA 2018](#)), a comparison of the NHS-supplemented placebo group (2:1 NHS to placebo) will also be performed at Month 12 versus the high-dose ifetroban ITT and PP populations for CMR parameters.

Summary statistics for other endpoints will be presented for both the ITT and PP Populations.

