5.1 Background Information

5.1.1 Duchenne Muscular Dystrophy

Duchenne muscular dystrophy (DMD) affects approximately one of every 3,300 male births worldwide ([Quinlivan 2009](#)) and is caused by the complete absence of the sarcolemmal protein dystrophin as a result of anomalies in the X-linked DMD gene. Loss of dystrophin leads to inexorable damage to skeletal and cardiac muscle, with cardiomyopathy increasingly recognized as a major cause of death ([Romfh 2010](#)). Due to ongoing muscle damage, patients with DMD have markedly elevated serum levels of the muscle protein creatine kinase (CK), which may be 10× to over 100× the normal limit, and an elevated CK level is a diagnostic sign ([Konagaya 1986](#)). There is currently no cure for DMD. Current treatment is limited to the management of symptoms which is fueling investigations aimed at targeting the genetic defect. Several therapies are in various stages of development, including utrophin up-regulation, stop codon read-through therapy, viral gene therapy, cell-based therapy and exon skipping. These have mainly focused on improving skeletal muscle function without addressing the cardiac aspects of the disease, which may aggravate cardiomyopathy. For this reason, preclinical and clinical focus on improving heart function is essential.

The absence of dystrophin in the heart renders cardiomyocytes more sensitive to stretch-induced damage. This results in increased levels of intracellular calcium, thereby activating calpains and proteases that consequently degrade contractile proteins, promoting cellular death and fibrosis, all contributing to the development of cardiomyopathy ([D'Amario 2017](#); [van Westering 2015](#)). Animal and human data demonstrate the myocardial damage is evident before functional decline such as a reduction in left ventricular ejection fraction (LVEF) ([Rafael-Fortney 2016](#)), endorsing a strategic treatment window for initiating cardioprotective treatment at earlier stages of myocardial disease while EF is preserved. LV systolic strain measured by cardiac magnetic resonance imaging (CMR) is a more sensitive measure of cardiac function, has high reproducibility ([Soslow 2016](#)) – a critical feature when testing hypotheses in patients with rare diseases to support efficient sample size reductions – and is abnormal in even the youngest boys with DMD well before EF drops ([Hor 2009](#)). Eplerenone was recently shown using CMR to attenuate the decline

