7.3.2 Exclusion Criteria

Individuals who meet any of these criteria are not eligible for enrollment as study subjects:

1. Clinically significant illness other than DMD
2. Clinically significant laboratory abnormality not associated with DMD
3. Major surgery within six weeks prior to the first dose of study drug, or planned surgery during this study which would interfere with the ability to perform study procedures
4. Require antiarrhythmic therapy and/or initiation of diuretic therapy for management of acute heart failure in the last 6 months
5. A LVEF of < 35% by CMR and/or fractional shortening of < 15% based on (ECHO during screening
6. A known bleeding disorder or has received anticoagulant treatment within two weeks of study entry

7. Allergy to gadolinium contrast or known renal insufficiency defined as abnormal cystatin C or creatinine above the upper limit of normal for age. The male serum reference ranges as follows:
 - Age 7-9 years - 0.2 - 0.6 mg/dL
 - Age 10-11 years - 0.3 - 0.7 mg/dL
 - Age 12-13 years - 0.4 - 0.8 mg/dL
 - Age 14-15 years - 0.5 - 0.9 mg/dL
 - Age 16 years or older - 0.8 - 1.3 mg/dL
8. Non-MR compatible implants (e.g. neurostimulator, automatic implantable cardioverter-defibrillator [AICD])
9. Subjects who participated in a therapeutic clinical trial within 30 days or five half-lives (whichever is longer) of study entry
10. Any other condition that could interfere with the subject's participation

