9 SUBJECT DISCONTINUATION AND STUDY OR SITE TERMINATION

9.1 Subject Discontinuation

Subjects will be encouraged to complete the study; however, they may voluntarily withdraw at any time. The Investigator will provide a report in the CRF describing the reason for discontinuation. If a subject withdraws before completion, every effort should be made to complete the assessments scheduled during the final scheduled assessment.

A subject may be terminated early from the study for the following reasons:

- The subject elects to withdraw consent from all future study activities, including follow-up.
- The subject is “lost to follow-up” (i.e., no further follow-up is possible because attempts to reestablish contact with the participant have failed).
- The subject dies.
- The subject develops a medical condition or is started on new medication(s) prohibited by the study or not previously mentioned in the list of prohibited medications that, in the opinion of the investigator, may pose additional risks from participation in the study, may interfere with the subject’s ability to comply with study requirements or that may impact the quality of the data obtained from the study.

Subjects who are prematurely terminated from the study will be followed to monitor safety for a minimum of 30 days or until resolution of the disqualifying event, whichever is longer, or until the Independent Safety Monitor, the CPI Director of Medical Affairs and the Principal Investigator determine that the follow-up is complete.

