11.7 Methods for Handling Missing Data

All missing data will be queried. Missing data which are not retrievable through queries will not be imputed. The only exception to this is one supportive analysis with missing LVEF at Month 12 imputed by LVEF at Month 6; subjects missing LVEF at both Month 6 and Month 12 will be excluded from this supportive analysis.

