## 4.2 Missing Data

For the primary endpoint and key secondary efficacy endpoints, missing data will not be imputed in the primary analyses. A supportive sensitivity analysis for the Month 12 LVEF endpoint will be conducted where missing LVEF values at Month 12 will be imputed using Month 6 values, if available. Subjects missing LVEF at both Month 6 and Month 12 will be excluded from this supportive analysis. For long-term analyses in the open-label extension, subjects missing data at key timepoints (Month 24, Month 36) will be excluded from the respective analyses. No other imputation will be provided for any endpoint.

Since LVEF is a key efficacy endpoint, the pattern of missing data will be carefully evaluated to assess potential bias. The frequency and reasons for missing LVEF measurements will be

summarized by treatment group to determine whether missingness might be related to treatment or disease progression. If systematic differences in missing data patterns are identified between treatment groups, additional sensitivity analyses may be conducted using multiple imputation methods that account for the potential relationship between the likelihood of missing data and the unobserved outcomes. This would involve creating multiple complete datasets based on observed covariates and outcomes, analyzing each dataset, and combining results according to Rubin's rules. These additional analyses would be considered exploratory and would be used to evaluate the robustness of the primary analysis approach.

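### The Month 12 LVEF and strain tests drop subjects who die or cannot have CMR for a cardiac reason, and no specified analysis counts these as bad outcomes

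*Protocol*

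**What the plan says.** **Main analysis.** Protocol 11.8.3 states that comparisons of change in LVEF and strain at Month 6 and Month 12 "will be performed for the ITT and PP Populations using the Wilcoxon rank sum test". SAP 6.2.1 names the same test for each dose against placebo, on whole arms. Protocol 11.7 adds: "Missing data which are not retrievable through queries will not be imputed". SAP 4.2 likewise imputes nothing in the main analysis. A subject without a Month 12 CMR is therefore not in the Month 12 test.

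**Supportive analysis.** There is one firm alternative, for LVEF only. Protocol 11.8.3 gives it as "A supportive analysis with missing LVEF at Month 12 imputed by LVEF at Month 6" and adds that "subjects missing LVEF at both Month 6 and Month 12 will be excluded from this supportive analysis". In the SAP's wording, "missing LVEF values at Month 12 will be imputed using Month 6 values, if available". Month 6 CMR is optional, with ECHO if it is declined (Protocol 8.1.2), and neither document says whether an ECHO value may be carried forward. Strain has no supportive analysis.

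**Other rules.** SAP 4.2 allows exploratory multiple imputation if missingness differs systematically between arms. SAP 3.3 prescribes LOCF for subjects who stop treatment before week 52, which contradicts SAP 4.2 and Protocol 11.7.

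**Events that remove the scan.** Protocol 9.1 lists "The subject dies" among the reasons for leaving the study. Protocol 7.3.2 excludes non-MR-compatible implants at entry and names the AICD as an example, but nothing covers one received on study. Neither document says how death or cardiac loss of the scan enters the efficacy comparison.

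**The concern.** Protocol 5.1.1 describes "cardiomyopathy increasingly recognized as a major cause of death", and half the planned sample is advanced stage (current or historical LVEF 35-45%). In this population a scan lost to death or cardiac deterioration is itself a cardiac outcome. Removing these subjects from placebo hides benefit; removing them from an ifetroban arm creates apparent benefit.

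The supportive analysis does not repair this. A subject who dies of heart failure at Month 9 with a Month 6 scan is scored at the Month 6 value. LOCF under SAP 3.3 does much the same. The multiple imputation in SAP 4.2 is optional, and it would give a deceased subject an LVEF rather than count the death.

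The test already works on ranks, so these outcomes can be ordered below all observed changes without inventing an LVEF.

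**Working it through.** **Inputs from the documents.** Effect size 1.6 SD, normal outcomes, two-sided 0.05 and 8 per arm within stage (Protocol 11.1; SAP 3.4). Two stages of 8 give 16 per arm for the whole-arm test.

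**Assumptions.** The documents give no number of deaths or unscannable subjects. I take 1 or 2 losses in one arm and assume that they are the subjects with the worst Month 12 change, which is the most informative case. An effect of 1.0 SD is added to show a smaller effect. For carry-forward, the 12-month change is the sum of two equal half-year increments.

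**Plan's own figures, 8 v 8, 1.6 SD.** The noncentral t gives 84.5% (stated: above 85%, so marginally short). The exact Wilcoxon by simulation gives 82% (stated: above 80%, reproduced).

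**Method.** U is the number of active-placebo pairs in which the active subject has the better change. It is compared with the exact critical value for the numbers analysed. Lost subjects are (a) dropped, (b) scored at Month 6, or (c) ranked below every observed change.

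**No true effect: chance of a false win for the drug (nominal 2.5%)**

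| Arms | Worst active lost | Dropped | Month 6 carried | Worst rank |
|---|---|---|---|---|
| 16 v 16 | 1 | about 5% | 2.9% | 1.7% |
| 16 v 16 | 2 | 8.4-8.6% | 4.1% | 1.0% |
| 8 v 8 | 1 | 5.2% | 3.8% | 0.9% |
| 8 v 8 | 2 | 9.7-10.1% | 4.6% | 0% |

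At 16 v 16, dropping 1 or 2 active subjects creates a spurious mean difference of 0.12 or 0.22 SD. If both arms lose their worst 1 or 2, the mean difference stays at zero and the rate is 3.0% or 3.8%.

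**True effect: power**

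| Arms, effect | No loss | 2 placebo lost, dropped | 2 placebo lost, worst rank | 2 active lost, dropped | 2 active lost, worst rank |
|---|---|---|---|---|---|
| 16 v 16, 1.6 SD | 98.8% | 96% | 99% | 99.7% | 96% |
| 16 v 16, 1.0 SD | 75% | 59% | – | – | 61% |
| 8 v 8, 1.6 SD | 82% | 58-59% | 83-84% | 93% | 0% |

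At 8 v 8 and 1.6 SD, one placebo loss gives 69% if dropped. One active loss gives 89% if dropped and 64% with worst rank. The zero in the table is arithmetic: with two of 8 active subjects ranked last, U is at most 6 × 8 = 48, and 51 is needed.

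**How much of the 8 v 8 loss is only sample size.** Losing 1 or 2 placebo subjects at random gives 75.5% or 72.5%. So 82 − 75.5 = 6.5 of the 13 points lost with one subject, and 82 − 72.5 = 9.5 of the 24 points lost with two, come from the smaller sample.

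**The case against.** **The plan has safeguards.** Protocol 8.1 asks for all End of Treatment assessments at premature discontinuation, and 9.1 asks for every effort at withdrawal. A subject who leaves with heart failure may therefore have a scan. Entry requires stable cardiac function, no heart-failure admission in 12 months and LVEF of at least 35%, which makes loss within a year less likely. SAP 4.2 summarises missing LVEF by arm and reason, and SAP 7.1 tabulates deaths. This stands in part: any scan obtained should be used. But no scan follows a death, neither document says whether an early End of Treatment scan counts as the Month 12 value, and a safety table does not correct the efficacy test.

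**Three stronger readings are tempting, and the documents do not support them.**

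- *That the planned test falls from 82% to 58% power.* Those are 8 v 8 figures. Eight per cell is the sample-size basis, while the specified tests compare whole arms and stage is an exploratory subgroup (SAP 6.5).
- *That losing 2 of 8 is the Protocol's own 25% dropout.* The 25% covers all causes and all arms and is used to recruit 60. Eight per cell (48/6) is the target after dropout.
- *That the Type I error is 8.6% or 10%.* Those rates are conditional on all losses falling on the worst subjects of the active arm. Where one loss mechanism acts equally on both arms under the null (worst 6% to 25% unobserved), the one-sided rate is 2.1-2.5%.

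**The remedy has a cost.** When active subjects are lost, worst rank can remove most or all of the power in small cells. This stands, and it is why the analysis should be supportive only.

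**Conclusion.** The gap is real. The Month 12 LVEF and strain tests omit subjects lost to death or cardiac unscannability, the one firm supportive rule scores LVEF from before the event, strain has nothing, and SAP 3.3 contradicts SAP 4.2. The bias has no fixed direction: it favours whichever arm loses more such subjects.

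At 16 v 16 the effect is modest for power at 1.6 SD (98.8% to 96%) and substantial at 1.0 SD (75% to 59%). The chance of a false win rises to about 5% or 8.6% when 1 or 2 of the worst active subjects are lost. All of this rests on assumed losses with the most extreme selection; with no such losses there is no bias. LVEF and strain are secondary endpoints and the primary endpoint is safety, so the change is advisable rather than essential.

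**What to change.** Before database lock and unblinding, amend Protocol 11.7 and 11.8.3 and SAP 4.2:

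1. Add a supportive worst-rank Wilcoxon analysis of Month 12 LVEF and strain, reported beside the observed-case test, which stays as it is.
2. Rank death, or absence of a usable Month 12 or End of Treatment CMR for a documented cardiac reason, below every observed change, with death lowest.
3. Where an End of Treatment CMR was obtained from a living subject, use that value.
4. Do not carry Month 6 LVEF forward after death or cardiac loss. Keep that rule for scans missing for non-cardiac reasons.
5. Reconcile the LOCF statement in SAP 3.3 with SAP 4.2.

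The cost is wording and a few lines of code. No new data are needed, because SAP 4.2 already calls for the reasons for missing LVEF. The plan should state the downside: the result is a composite rank, and it loses power when losses fall in the active arm. With 2 active losses at 16 v 16, power is about 96% at 1.6 SD and 61% at 1.0 SD. At 8 v 8 and 1.6 SD it is 64% with one loss and 0% with two.

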11.2.2 Intent-to-Treat Population

The Intent-To-Treat (ITT) Population will consist of all treated subjects with at least one post-baseline assessment.

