11.2.3 Per Protocol Population

The Per Protocol (PP) Population will consist of all subjects in the ITT population with no major protocol violations, including violation of inclusion or exclusion criteria or insufficient dosing where the latter includes missing more than 2 consecutive weeks of dosing for any reason or missing >20% of prescribed doses between consecutive visits.

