11.5 Historical Comparator

Data collected from an FDA-funded DMD NHS will be used as a historical comparator/supplemental placebo group ([Soslow 2023](#)). The NHS utilized as a comparator is an ongoing, multi-year, multicenter study evaluating the natural progression of DMD. Eligibility is broad based on DMD diagnosis, and endpoints collected mirror endpoints collected for CPI-IFE-007 except patient-reported outcomes (PedsQL). NHS visits are scheduled yearly, and demographic, baseline characteristics, medical history, and concomitant medication information is collected at each visit along with CMR, PFTs, QMT, and accelerometry. Patients from the NHS will be selected at a 2:1 ratio (NHS to placebo) using propensity score matching (PSM) based on baselined LVEF, age, and background DMD therapy with consideration for other relevant cardiac medications (ACEi, ARB, beta-blockers, ARNI, aldosterone receptor antagonists, diuretics, calcium channel blockers. Matched NHS patients will be added to the CPI-IFE-007 placebo group from the 12-month double-blind study to create a supplemental, representative placebo group of a larger size for Month 12 efficacy analyses. For the open label extension, a historical comparator group will be formed from NHS patients selected at a 2:1 ratio (NHS to open label high-dose ifetroban) using PSM as described above. The NHS comparator group for the open label extension will be compared with open-label high-dose ifetroban patients at Month 12, Month 24, and Month 36.

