## 6 EFFICACY ANALYSIS

The efficacy analyses in this study incorporate natural history data as a supplemental comparator, a strategy supported by recent research and regulatory perspectives in rare disease settings. This approach has demonstrated validity in DMD specifically ([Goemans 2020](#)), where matched external controls have shown utility in drug evaluation, especially when disease progression is relatively well-characterized. The FDA has acknowledged the importance of natural history data in rare disease clinical development and real-world evidence frameworks. Research by Soslow et al. ([2023](#)) supports the application of natural history data while acknowledging its limitations and necessary methodological considerations. The propensity score matching methodology employed in this study aims to address potential selection bias and confounding factors when incorporating this external data.

All hypothesis tests will be performed at the 0.05 level. Analyses of secondary efficacy variables will be performed using the ITT and PP population only. Summary statistics will be presented for all analyses of efficacy variables.

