#### **14.3.6 Analysis Population**

For the DB period, only high dose active and placebo subjects with Month 12 evaluable cardiac efficacy data will be included in the analysis.

For OL, all ifetroban treated subjects in the ITT population will be matched with natural history data.

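### The natural-history-supplemented Month 12 comparison is also planned on the high-dose Per Protocol set, whose dosing exclusions cannot be applied to the natural-history controls

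*Protocol*

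**What the plan says.** Protocol 11.8.3 plans the Wilcoxon comparisons of the randomised arms on ITT and PP. It then adds a Month 12 analysis that sets the placebo group, enlarged with NHS patients, against ifetroban: "versus the high-dose ifetroban ITT and PP populations for CMR parameters". The ITT and PP labels are attached to the high-dose side; the comparator carries none.

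ITT is "all treated subjects with at least one post-baseline assessment" (Protocol 11.2.2). PP is the part of ITT with "no major protocol violations, including violation of inclusion or exclusion criteria or insufficient dosing", the last of these covering "missing more than 2 consecutive weeks of dosing for any reason or missing >20% of prescribed doses between consecutive visits" (Protocol 11.2.3).

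Under Protocol 11.5, NHS patients are added to the randomised placebo group at two per placebo subject.

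The SAP handles this comparison in Appendix 3. Section 14.3.6 says that "only high dose active and placebo subjects with Month 12 evaluable cardiac efficacy data will be included in the analysis" and does not mention PP. Section 6 says generally that "Analyses of secondary efficacy variables will be performed using the ITT and PP population only". Sections 4.4.4 and 8 declare no change from the protocol's analyses. Section 4.5.3 labels the NHS comparisons supplementary.

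**The concern.** The dosing part of PP is a filter on behaviour after treatment starts. Between randomised arms it at least applies to both sides. Against NHS patients it cannot: they have no study doses to miss. A high-dose subject who goes without drug for more than two weeks, for whatever reason, leaves the PP comparison. An NHS patient with a similar clinical course stays, provided he is alive with complete cardiac data.

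If missing doses goes with a worse cardiac course, the PP version can show a difference for an inactive drug. Printed beside the ITT version, it could be taken as independent support for it.

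There is also a matching problem. SAP 4.5.2 matches NHS patients to high-dose subjects, and no re-matching is described for a PP subset. Removing high-dose subjects afterwards leaves their matched controls in place and can disturb the balance that the matching was meant to create.

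**Working it through.** **The plan's own figures.** The documents give no PP exclusion rate and no adherence–outcome figure. The only related number is the power statement (Protocol 11.1): 8 per arm within a disease stage, effect size 1.6, two-sided 0.05. The noncentrality is 1.6 × √(8/2) = 3.2 on 14 degrees of freedom, giving t-test power of 84.5% (stated: above 85%). Simulated Wilcoxon power is 82.2% (stated: above 80%). The point does not depend on these; they supply 1.6 SD as a yardstick.

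**Inputs from the documents.** 16 high-dose and 16 placebo subjects (8 per stage, Protocol Table 7-1). NHS patients: 2 × 16 = 32 (Protocol 11.5). Comparator: 16 + 32 = 48, of which 32/48, two thirds, are NHS. Test: Wilcoxon rank sum, two-sided 0.05.

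**Assumptions.** No drug effect; LVEF changes normal with SD 1; PP removes the 2 least adherent of 16 high-dose subjects (12.5%); correlation r between adherence and LVEF change.

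**Bias, high-dose side filtered only.** The two lowest of 16 standard normal values have expectations −1.766 and −1.285, summing to −3.051. The 14 who remain therefore average 3.051/14 = 0.218 SD on adherence, and 0.218 × r on LVEF change. The unfiltered comparator averages 0.

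- r = 0: 0
- r = 0.3: 0.218 × 0.3 = +0.07 SD
- r = 0.5: 0.218 × 0.5 = +0.11 SD
- r = −0.3: −0.07 SD (simulated −0.06)

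**Bias, placebo subjects also filtered.** The comparator becomes 14 placebo + 32 NHS = 46, with mean 0.218 × r × 14/46 = 0.066 × r. The difference is (0.218 − 0.066) × r = 0.152 × r, or +0.05 SD at r = 0.3 and +0.08 SD at r = 0.5 (simulated 0.05 and 0.07). It does not vanish, because the NHS part stays unfiltered.

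**False rejection, 2 of 16 removed, high-dose side only.** Simulation gives about 5.6% at r = 0.3 and 6.4% at r = 0.5. Separate runs of 6,000 to 20,000 trials ranged over 5.1–5.6% and 5.8–6.6%. At r = 0 the rate is near nominal, about 4.8%.

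**Sensitivity to the assumed exclusions** (6,000 runs per cell, high-dose side only):

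| Removed | r = −0.3 | r = 0.3 | r = 0.5 |
|---|---|---|---|
| 3 of 16 | −0.10 SD; 5.8% | +0.09 SD; 5.6% | +0.15 SD; 7.9% |
| 5 of 16 | −0.15 SD; 6.8% | +0.14 SD; 7.0% | +0.25 SD; 11.9% |

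**Randomised contrast.** When PP is applied to both randomised arms and adherence works alike in each, the simulated bias is about 0 in every cell.

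**The case against.** The strongest reply is that the SAP has already settled the matter. Protocol section 11 leaves details to the SAP, and SAP 14.3.6 specifies Month 12 evaluable subjects without PP. The groups listed in SAP 14.3.7 include no PP version, and SAP 6.2.1 names ITT for the LVEF tests. This is a fair reading, but the protocol sentence is explicit, SAP section 6 keeps PP for secondary efficacy, and the SAP declares no change. The PP version either stands or is in conflict between the documents.

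The reply is right on several stronger claims that a reader might infer:

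- *That the result tilts towards ifetroban.* No passage links missed doses to LVEF decline. Doses may be missed for reasons unrelated to the heart, for instance the fasting requirement in Protocol 7.6. The sign depends on r.
- *That only the ifetroban side is trimmed.* The documents do not say whether the randomised placebo subjects in the comparator are PP-restricted. NHS controls pass filters of their own: alive, complete cardiac data, no history of heart failure (SAP 14.3.2). Excluding those who died or lack data may make the controls look better. None of this is an adherence filter, so the asymmetry remains, but the net direction is not established.
- *That the 25% dropout figure shows how many PP would remove.* The target of 48 is already net of dropout (Protocol 11.1 and 7.1), and subjects without Month 12 data are missing from the unimputed ITT comparison too. The SAP also states 10% (section 3.4). Dropout therefore says nothing about exclusions beyond ITT.

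The 48 controls are one reading; SAP 14.3.1 writes the 2:1 ratio as placebo to high-dose. A different comparator size leaves the high-dose-only bias of 0.218 × r unchanged but alters the rejection rates.

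**Conclusion.** The point holds as a difference in selection: the protocol applies a post-baseline dosing filter to one side of a comparison in which about two thirds of the other side cannot undergo it. Its direction and size are not fixed by the documents.

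With 2 of 16 removed and r of 0.3 to 0.5, the effect is modest: 0.07 to 0.11 SD is about 4% to 7% of the 1.6 SD design effect (0.07/1.6 and 0.11/1.6). The exclusion count, the correlation and normality are all assumptions. The larger values in the table need heavier exclusions that nothing in the documents supports.

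The randomised comparisons, the ITT version of the NHS comparison and the primary safety endpoint are untouched. It is still worth correcting: the PP version adds no like-for-like information, and Protocol 11.8.3 and SAP 14.3.6 do not agree on the population.

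**What to change.** In Protocol 11.8.3 and SAP 14.3.6, define the NHS-supplemented comparison on ITT high-dose and ITT placebo subjects with Month 12 cardiac data, and delete the dosing-based PP version. This also settles which set the placebo part uses.

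If a PP-type version is wanted, restrict its exclusions to baseline eligibility violations that can be checked in both studies. Apply them to high-dose, placebo and NHS subjects alike, do so before matching, and label the result descriptive.

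Keep the dosing-based PP set for the randomised comparisons.

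The cost is wording in two documents. One supplementary analysis is lost or narrowed, and the sponsor gives up a comparison of adherent subjects with natural history.
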